### Baseline and Final Follow-up

Demographics: Demographic data including age, race, ethnicity, marital status, educational attainment, annual family income, and household roster; and psychiatric illness history will be collected from the patient at baseline only.

Phone data plan: Phone data plan information will be collected from each patient's recent phone bill brought to the baseline assessment. We will also collect their phone number.

Psychopathology, Substance Abuse, Cognitive Deficits, Functioning: Psychopathology will be measured using the Brief Psychiatric Rating Scale (BPRS) at both baseline and 9 month follow-up. Psychopathology will be measured using the Brief Psychiatric Rating Scale (BPRS). We will use the BPRS Positive Symptoms Factor (psychosis), Activation Factor (mania), and Affect Factor (depression) (9 items total).

Cognitive deficits of SMI will be measured by brief assessment. We will assess verbal learning using the Hopkins Verbal Learning Test-Revised (HVLT-R), and processing speed using the Digit Symbol Coding Test at baseline only. Occupational, social, symptom-related and overall functioning will be assessed using the MIRECC GAF at baseline only, which has been validated in Veterans with SMI.

Housing Stability: Housing stability for the past 30 days will be assessed using the Residential Time-Line Follow-Back Inventory (RTLFB). The RTLFB has been used in prior research to collect retrospective housing history over a specified period of time among people who have experienced homelessness. All residences over 30 days will be recorded, and coded into one of 34 previously defined locations, which will be further categorized as "stable" (e.g., own apartment, room or studio apartment in a supportive housing program, transitional housing, group home, boarding home) versus "unstable" (e.g., living on the streets, in public places, in emergency shelter-type accommodations) settings, using established methodology. The number of days spent in any of the locations categorized as "stable" or "unstable" will be summed and divided by the total number of days of residency reported at the interview,

and reported as a percentage. RTLFB has been demonstrated sensitive to change. This will be collected at baseline only.

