We study digital phenotypes that are informative as predictors of behaviors and symptoms. These include both short- and long-term behavioral data, i.e. what an individual has done recently and how their behavior and symptoms have changed over time. There will be multiple real time data streams collected that will be continuous and intermittent sequence activities to assess behaviors (Table 1). Even though the data can be represented as a function of time  $t$ , they are being collected at vastly different frequencies and durations, and with different noise and error rates. Thus, we use a two-phase analytics pipeline of modeling. In phase 1, we conduct data preprocessing that derives features capturing events from the data collected. In phase 2, we conduct predictive analytics using machine learning that models correlations between sensor and phone utilization data, and behavioral assessments and symptoms.

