From the project's mobile app, we obtain highly detailed patient level information over a 9 month follow up period and transmit it to the server database. In the data preprocessing phase, we reduce these mobile data to continuous summaries that retain more information than categorical ones. Sensor and utilization data are captured at varying frequencies for the different domains. For measures that are updated in seconds and minutes, we summarize data using activity profiles (over a day or a week), defined as the amount of time the person spends at an activity level (e.g., above a certain threshold) or engaged in an activity (e.g., walking, exercising, riding in a motor vehicle). Movement measured through the accelerometer will be transformed to an activity profile by defining activities from no movement to faster movement (using thresholds). Light and sound levels will be thresholded from low to high and the amount of time spent at each level captured. In this way, problems with temporal alignment of data are mitigated, transforming data into densely measured functional data, conceptualized as longitudinal functional data. Here the profile constitutes the functional observation varying over levels (summarizing over a day or a week) and days/weeks constitute the longitudinal repetitions. For measurements summarized over days (e.g., total phone calls, total hours of sleep), data are conceptualized as longitudinal data. We also include static patient measures from baseline that could improve the accuracy of models, such as demographics, prior medication adherence, housing status, psychiatric symptoms, cognitive deficits associated with SMI, and social and occupational functioning.

For data obtained from smartphones, an issue that will arise frequently is missing data. When adjusting for missing data in creating activity profiles, we will consider various approaches. One approach is a similarity assumption which states that the proportion of time that a participant spends at a given activity level during the observed times is similar to the proportion in the unobserved times. This is similar to a missing at random assumption in longitudinal data analysis. For example, time spent at different

activity levels (activity profile) could be rescaled to include time over unobserved periods as well. Another approach is to use the planned machine learning approaches to also evaluate missing data patterns.

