In Aim 3 we develop individualized estimates of sociability, activities and sleep. We will aggregate daily mobile data on a weekly basis to predict behavioral measures that are also obtained weekly. Summary statistics such as mean, variance, min, or max will be used for aggregation as deemed appropriate. We will then employ various machine learning algorithms to build, train, and select prediction models for each of the patient behavioral assessment domains using features of sensor and phone utilization data (Table 1). Model development will proceed in three stages. First, we will utilize methods of unsupervised learning to cluster sensor and phone utilization data and extract features to reduce the dimensionality. Second, we will explore a number of supervised learning procedures to build candidate prediction models for patient behavioral assessments. Finally, we will use cross-validation to estimate the out-of-sample performance of the prediction models, and to select best model(s) from among the candidates.

To reduce the number of features upon which to build the prediction models, while preserving the maximum amount of information, the first strategy is to use principal component analysis (PCA). PCA reduces the dimensionality of a data set by identifying linear combinations of the features, the principal components, which maximize variability while remaining mutually uncorrelated. Building the models using fewer candidate features reduces the risk of overfitting, and using the principal components in place of the original features prevents problems of multicollinearity. The second dimension reduction strategy is to use FDR (false discovery rate) threshold. FDR-based thresholding gives an optimal way of adapting to unknown sparsity (only a small number of effects are significantly large) and may be viewed as an estimation procedure with an appropriate penalization scheme accounting for the number of selected variables.

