Given the reduced number of features, various supervised machine learning algorithms will be used to train prediction models for patient behaviors and symptoms. At the preliminary analysis stage, a set of supervised learning algorithms will be explored to evaluate cross-sectional associations between mobile data features and patient behavioral assessments, with the goal of narrowing down the pool of candidate predictors. First, we will consider random forests. A random forest is a collection of decision trees, each built using a random sample of features, and trained on a bootstrap sample from the original data. Random forests are useful for identifying complex interactions among features due to the use of decision tree learning, while protecting against overfitting by means of bootstrap aggregation. Second, we will consider support vector machines (SVM). SVM is a method of supervised learning which classifies instances into categories by estimating a hyperplane that separates instances belonging to different classes. SVM may be used if the outcomes of interest, behaviors and symptoms, can be meaningfully categorized (e.g., high vs. low). Selected predictors from these approaches will be used in the next step of the model building process that takes into account the temporal correlation and time series nature of mobile data and patient assessments. We will use hidden Markov models to predict patients' current behaviors and symptoms based on current features and past patients' behaviors and symptoms. We view patients' features as observed states, and patients' behaviors and symptoms are hidden states that enjoy the Markov property. We will also use linear or generalized linear mixed effects models to predict patient behavioral assessments using selected features from the preliminary stage, while taking into account within-patient correlation in repeated measurements over time.

Models developed using supervised machine learning methods will be evaluated in terms of out-of-sample predictive performance using leave-one-out cross-validation (LOOCV). For time series modeling, models will be trained on times 1, ..., t-1, and evaluated on time t, for each time t. For cross-sectional modeling, models will be trained on all but patient i, and evaluated on patient i, for each patient i. Performance will be averaged across hold-out times/patients to obtain a LOOCV estimate of

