generalization error. Quadratic loss will be used to evaluate prediction error. The selected model will be the one that minimizes LOOCV mean squared error.

In Aim 4, outcome data are collected weekly for each patient on three scales (psychosis, mania, depression). These scales each have a range of 1 to 7. The primary outcome will be the scale indicating the most severe symptoms in a 2-month window. We will evaluate the association between mobile data features identified in Aim 3 with this primary outcome using a mixed effects model to accommodate within patient data correlation due to repeated measures. Specifically, we will consider feature data from fixed time windows preceding the most severe symptoms. The outcome data distribution will be examined prior to model fitting, and an appropriate link function will be used in the mixed effects model.

Sample size and power considerations: In Aim 3, we extract features of mobile sensor and phone utilization data to estimate behaviors in the domains of sociability, activity, and sleep. The selected features should have a high correlation with behaviors to be a good estimate. Of 100 participants enrolled, assuming 30% attrition, we expect to have complete data on 70 participants (and substantial longitudinal data for a larger group). This sample size will provide over 95% power to detect a correlation of at least 0.50 at the significance level 0.05 using a two-sided test. In Aim 4, our inclusion criteria select for greater than average symptom risk, so we anticipate substantial symptoms. Previous research on 21 patients with SMI for a median of 134 days found that sensing data predicted symptom indicator scores with correlations in the range of 0.5 to 0.8. Given possible confounders, and since our sample may be more heterogeneous than prior research, the correlation in our study is anticipated to be lower than what was reported previously. With 100 enrolled, and assuming 30% attrition, we will have over 85% power to detect correlations of at least 0.35 between predictors of interest and symptoms assessments at the significance level of 0.05 using a two-sided test.

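### The Aim 4 primary mixed model does not have to separate a patient's usual feature level from deviations from it, so a significant result may reflect stable differences between patients, not exacerbation

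*Combined protocol and SAP*

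**What the plan says.** All references are to the combined protocol and SAP.

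- **Aim.** The fourth objective, repeated in Data Analyses under Aims 3 & 4, is to study how well sociability, activity and sleep data pick up worsening of psychiatric symptoms. Data Collected from Mobile Application expects acute stress to show itself as altered behavior.
- **Aim 4 outcome and model (Data Analyses).** "The primary outcome will be the scale indicating the most severe symptoms in a 2-month window". Then: "We will evaluate the association between mobile data features identified in Aim 3 with this primary outcome using a mixed effects model". On timing: "Specifically, we will consider feature data from fixed time windows preceding the most severe symptoms". The stated reason for the mixed model is correlation among a patient's repeated measures. No random-effects structure, centering or patient-mean term is given.
- **Where the features come from (Data Analyses, Aim 3).** "Summary statistics such as mean, variance, min, or max will be used for aggregation as deemed appropriate". Candidate predictors are first narrowed by cross-sectional association with the behavioral assessments.
- **Text that helps.** The Aims 3 & 4 section says informative predictors include "how their behavior and symptoms have changed over time". It also says: "We also include static patient measures from baseline that could improve the accuracy of models, such as demographics, prior medication adherence, housing status, psychiatric symptoms". The baseline score exists: "Psychopathology will be measured using the Brief Psychiatric Rating Scale (BPRS) at both baseline and 9 month follow-up". A separate modeling step uses symptom history: "We will use hidden Markov models to predict patients' current behaviors and symptoms based on current features and past patients' behaviors and symptoms". None of these is written into the Aim 4 model for the primary outcome.

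**The concern.** An exacerbation is defined against the patient's own usual state. A patient who is always inactive and always symptomatic tells us nothing about whether a fall in activity precedes worsening. A random intercept allows for the correlation among that patient's windows, but it does not make the coefficient of an uncentered, time-varying feature a within-patient quantity. The coefficient remains a weighted average of two associations: do sicker patients usually behave differently, and does a patient's behavior differ from usual before a worse peak?

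If only the first holds, the Aim 4 result can be significant and be read as evidence that sensing identifies exacerbations, although no patient's behavior changed beforehand. What is at stake is the conclusion that the Aim 4 primary result can carry.

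**Working it through.** **1. The plan's own figure.** Inputs from Sample size and power considerations: 100 enrolled, 30% attrition, so 70 analyzed; r = 0.35; two-sided 0.05; power stated as over 85%. By Fisher z, power = Φ(atanh(0.35) × √(70 − 3) − 1.96) = Φ(0.3654 × 8.185 − 1.96) = Φ(1.031) = 84.9%; a noncentral t calculation gives 86.9%. The figure reproduces. It treats Aim 4 as one correlation in 70 patients and does not say whether the association is between or within patients.

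**2. Why the coefficient blends.** In a balanced random-intercept model with K windows per patient, the uncentered coefficient is

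β = w·β_within + (1 − w)·β_between, with w = I_W / (I_W + I_B),

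where I_W = S_W / σ²_e, I_B = S_B / (σ²_e + Kσ²_u), S_W and S_B are the within- and between-patient sums of squares of the feature, and σ²_e and σ²_u are the residual and random-intercept variances.

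Assumed, not in the documents: K = 4, one feature, one score per window, unit total variances, intraclass correlation (ICC) 0.5 for feature and outcome, between-patient r = 0.35, no within-patient link.

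- S_W = 70 × 3 × 0.5 = 105, so I_W = 105 / 0.5 = 210.
- S_B = 4 × 69 × (0.5 + 0.5/4) = 172.5, so I_B = 172.5 / (0.5 + 4 × 0.5) = 69.
- 1 − w = 69 / 279 = 0.247.
- β_between = 0.35 × 0.5 / 0.625 = 0.28, so β = 0.247 × 0.28 = 0.069.
- SE = 1/√279 = 0.060, so z = 1.16.
- Chance of significance = Φ(1.16 − 1.96) + Φ(−1.16 − 1.96) ≈ 21%.

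Simulating the same layout (500 runs per setting) gives 21%. With ICCs for feature/outcome of 0.7/0.5 and 0.7/0.7 it gives 39% and 28%. Adding a baseline symptom score brings the three settings to 14-22%. The deviation coefficient stays at 3-5%.

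**3. Closer to the planned outcome.** Further assumptions: 39 weeks, four non-overlapping 9-week windows, three normally distributed scales, outcome the highest score on any scale in the window, feature averaged over the 2 weeks before the peak, ICC 0.5, REML random intercept with a Wald test. There is no within-patient link. Ranges are across repeat simulations.

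| Between-patient r | Level feature, no covariates | Level feature + three baseline BPRS scores | Deviation term (with patient mean and baseline BPRS) |
|---|---|---|---|
| 0 | about 5% | about 5% | about 5% |
| 0.10 | – | 6-7% | – |
| 0.20 | – | 11-12% | – |
| 0.35 | 36-41% | 21-24% | 5% |
| 0.50 | 63-67% | 40-41% | 5% |

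(A dash means not computed.)

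**4. Sensitivity at r = 0.35, with baseline BPRS.** ICC 0.3 gives 23% and ICC 0.7 gives 17%. At ICC 0.5: one selected scale per patient 22%, scores rounded and bounded to 1-7 27%, autocorrelated weeks 21%, 30% missed calls 25%. The deviation term gives 4-6% throughout.

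**5. What the split does to power.** For a purely within-patient link of 0.10 / 0.20 / 0.35, the deviation term is significant in 20% / 58% / 98% of runs, against 15% / 47% / 91% for the level feature with baseline BPRS. With both links (between 0.35, within 0.20) the figures are 56% and 88%.

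**6. Limits of the split.** Centering on earlier weeks only, with the mean and baseline BPRS also in the model, gives 8.7% at r = 0.35, so the 5% depends on a mean taken over all of follow-up. Where the feature merely follows symptoms by a week or two, the deviation term is significant in 9-18% of runs, because only pre-peak feature data are compared.

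**The case against.** The strongest reply is that the model is under-specified, not wrong. Nothing fixes a single uncentered level feature. The joint Aims 3 & 4 text, like the opening summary, names change over time among the predictors, and it admits baseline symptoms to the models. A feature already expressed as change from the patient's own level would not have this problem. The opening summary also speaks of classifying individuals by risk group, which is a between-patient target. All of this stands. It is why the point is conditional on level features being used, and why the baseline-adjusted figures are the fairer ones.

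The size also rests on assumed inputs. The plan's 0.35 is not described as a between-patient correlation, and at 0.10 the effect is negligible. That stands too.

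What does not stand is that the general wording settles the matter. The Aim 4 model is the only one given for the primary outcome, and it requires neither change features nor the baseline score. One noisy baseline score does not capture a patient's usual level, so adjustment reduces the problem without removing it. The hidden Markov models are a separate step.

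A reader might go further and infer that the test has an inflated false-positive rate, or that a significant result would be spurious. The documents do not support that. In these scenarios a between-patient association truly exists, and with no link at all every model rejects at about 5%. The result misleads only if it is taken to show that exacerbations are identified.

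**Conclusion.** The concern holds in conditional form. The Aim 4 primary model does not require the usual level and the deviation to be separated. If level features enter it, a significant coefficient cannot by itself be attributed to behavior change before worsening.

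With no within-patient link, 70 patients, four windows and ICC 0.5, significance occurs in roughly 20-25% of runs at a between-patient correlation of 0.35 with baseline BPRS adjustment, about 11% at 0.20 and near 5% at 0.10. Unadjusted, the 0.35 figure is about 35-40%, or as low as 21% in the simpler one-score-per-window layout. The ICC, window layout, feature window and between-patient correlations are all assumptions; the direction held in every setting tried at 0.35 and 0.50.

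It should not be inferred that the plan ignores within-patient change or that its power figure is wrong: change features are mentioned, and the power figure reproduces. How the worst scale is chosen and how the windows are laid out are matters for clarification and are not part of this point.

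**What to change.** In the Aim 4 mixed model:

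1. Enter each feature as two terms: the patient's own mean over follow-up, and the deviation of the pre-peak value from that mean.
2. Include the three baseline BPRS factor scores (positive symptoms, activation, affect) as covariates.
3. Base any conclusion about exacerbations on the deviation coefficient, and report the between-patient coefficient separately under that name.
4. State three limits. A mean over all of follow-up uses data from after the peak, so this is a retrospective test of association. Any claim of prospective prediction must use past data only, under the train-on-earlier-times scheme already in Data Analyses. An analysis confined to peaks does not by itself exclude behavior that follows symptoms.

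The cost is a few sentences in the plan and a little code; the planned assessments already supply the data. The downside is that the deviation coefficient takes no credit for between-patient differences. When both links exist it is significant less often than the blended one, about 56% against 88% under the assumptions above. For a purely within-patient link it loses no power.
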